### Eligibility Criteria Diabetic Foot Ulcer (DFU):

#### Inclusion Criteria:

- 1. Male or female 21-80 years of age
- 2. Participated in the informed consent process and signed study specific informed consent document
- Willing and able to comply with study procedures, including study visits and study dressing regimens
- 4. Diagnosed as having Type 1 or Type 2 diabetes
- 5. HbA1c of  $\leq$  10%
- 6. Presence of a DFU, Wagner 1 or 2 (see **Appendix 7** for definitions), extending at least through the dermis provided it is below the level of the medial or lateral malleolus. Any wound that has been present for ≥ 6 months and hasn't previously been biopsied, a biopsy must be performed to exclude other skin conditions e.g. cancer for ulcers. Also, if a clinical

- suspicion of malignancy exists in the opinion of the Investigator, a biopsy should be performed regardless of duration of wound
- 7. The target wound will be located on the foot or ankle and will be the largest ulcer if two or more DFUs are present with the same Wagner grade and will be the only one evaluated in the study. If other ulcerations are present on the same foot, they must be more than 1 cm distant from the target wound
- 8. Target wound (i.e. current episode of ulceration) has been present for greater than 4 weeks prior to screening visit and less than 12 months, as of the date the subject consents for study
- 9. Target wound size ≥ 0.25 cm^2 to ≤ 150 cm^2 post debridement at Screening Visit and Treatment Visit Week 1/Randomization

#### **Exclusion Criteria:**

- 1. Subject with a BMI ≥65
- 2. Subject is medically unable to consent (due to head trauma, coma, etc.) or cognitively impaired (due to being mentally challenged, having Alzheimer's, etc.)
- 3. Subject is an active smoker
- 4. Subject has any history of fish allergy or a known sensitivity to any of the SOC materials which come into contact with the skin
- 5. Target wound(s) deemed by the investigator to be caused by a medical condition other than diabetes or subject has wounds secondary to a disease other than diabetes (e.g. vasculitis, neoplasms, or hematological disorders)
- 6. Ankle-Branchial Index (ABI) less than 0.80 or greater than 1.3
- 7. Presence of any monophasic waveforms
- 8. Subject has the following abnormal lab values: Albumin < 2.5 g/dL; Total Protein < 5 g/dL; BUN above 25 mg/dL; Creatinine > 3.0 mg/dL
- 9. The subject is unable to safely ambulate with the use of a study required offloading method
- 10. Any active cancer other than a nonmelanoma skin cancer; any previous cancer must be in remission for at least 1 year; bone cancer or metastatic disease of the affected limb, radiation therapy to the foot, or has had chemotherapy within the last 12 months
- 11. Subject has received within 28 days of screening a treatment which is known to interfere with or affect the rate and quality of wound healing (e.g., thrombolysis, systemic steroids, immunosuppressive therapy, autoimmune disease therapy, dialysis, radiation therapy, chemotherapy) to the foot or during the screening period or who are anticipated to require such medications during the course of the study
- 12. Subject on any investigational drug(s) or therapeutic device(s) within 28 days preceding randomization
- 13. History of radiation at the ulcer site (regardless of time since last radiation treatment)
- 14. Target wound has received hyperbaric therapy or wound dressings that include growth factors, engineered tissues, or skin substitutes within 28 days of randomization or is scheduled to receive treatment during the study (e.g., Apligraf, PriMatrix, AMNIOEXCEL (first generation), Regranex, Dermagraft, EpiFix, GraftJacket, OASIS, Omnigraft, or Integra BMWD
- 15. Presence of any condition(s) which seriously compromises the subject's ability to complete this study or has a known history of poor adherence with medical treatment
- 16. Osteomyelitis or bone infection of the affected foot as verified by x-ray within 30 days prior to randomization. (In the event of an ambiguous diagnosis, the subject will not be enrolled)
- 17. Suspected or confirmed gangrene or wound infection of the study ulcer, as evidenced by

tissue necrosis, redness, pain, and/or purulent drainage and/or receiving systemic antibiotics for the treatment of such

- 18. History of immunodeficiency or any illness or condition, other than diabetes, that could interfere with wound healing e.g., excessive lymphedema, end-stage renal disease, severe malnutrition, liver disease, aplastic anemia, Raynaud's Syndrome, connective tissue disorder, acquired immune deficiency syndrome, HIV positive, or sickle cell anemia
- 19. Subject has unstable Charcot foot or Charcot with bone exposed that could inhibit wound healing

#### Criteria for Evaluation of Efficacy and Safety

Objective efficacy endpoints comparing the Omeza® Products Bundle vs Standard of Care are:

- Percent change from baseline in target wound measure at Week 4, Week 8 and by Week 12/ End of Study.
- Ulcer size closure rate at Week 4, Week 8 and by Week 12/ End of Study.
- Time to maximum closure or complete closure.
- Incidence of DFU and VLU subjects healing at Week 12/ End of Study.

Safety and tolerability will be evaluated by assessing treatment-emergent adverse events, compliance, concomitant medications, Labs, Vital Signs and Physical Examinations.

#### **Vascular Assessment**

Ankle-Branchial Index (ABI) of ulcers/wounds will be measured using the MESI ABPI MD device. It is an automated machine that uses oscillometry and volume plethysmography for accurately calculate the ABI. This device can also automatically collect pulse volume waveform readings (mediUSA).

#### **Method of Target Wound Measurement and Photography**

Swift Medical wound platform will be used for the measurement and imaging of ulcers/wounds (SWIFT MEDICAL Inc.).

#### Statistical Methods

Efficacy analyses will be conducted under the intent to treat principle. Analyses will be performed on each of the two indications (venous leg ulcers and diabetic foot ulcers) and overall. Analyses to include the primary endpoint of:

- % change from baseline (Treatment Visit Week 1) in ulcer measure at Treatment Visit Week 4,
   Week 8 and by Week 12/End of Study using a mixed model repeated measure (MMRM)
- Ulcer size closure rate will be reported at Treatment Visit Week 4, Week 8 and by Week 12/End of Study.
- Time to maximum closure or complete closure will be assessed using Kaplan-Meier estimation, with medians, quartiles, and 95% confidence intervals (CIs).
- Incidence of DFU and VLU will be analyzed by comparing the proportion of subjects healing at week 12/End of Study.

Further analysis may also be conducted using age category as a subgroup.

Descriptive statistics will be provided for subject demographics, safety, and exposure data and will include the number of observations, mean, standard deviation (SD), median, and range for continuous variables and number and percent for categorical variables; 95% CIs will be presented where appropriate.

#### Sample Size Analysis:

The power of the study is computed for the primary endpoint of "percent change from baseline in target wound measure by Week 12" comparing the two means. The combined sample size of 78 subjects (randomized 2:1) will provide over 80% power to detect a difference of about 14 units (percent change from baseline in wound measure by Week 12), assuming a standard deviation of 20 units, and a 2-sided significance level of 5%.

### **List of Abbreviations**

Abbreviation or	Definition:
Term	
ABI	Ankle Branchial Index
ADL	Activities of Daily Living
AE(s)	Adverse Event(s)
CI	Confidence Interval
CFR	Code of Federal Regulations
CLU	Chronic Lower Extremity Ulcers
CRF(s)	Case Report Form(s)
CRO	Clinical Research Organization
CSR	Clinical Study Report
DFU	Diabetic Foot Ulcer
eCRF	Electronic Case Report Form(s)
EDC	Electronic Data Capture
FDA	U.S. Food and Drug Administration
GCP	Good Clinical Practice
GMP	Good Manufacturing Practices
HIPAA	Health Insurance Portability and Accountability Act
ICF	Informed Consent Form
ICH	International Conference on Harmonization
IEC	Independent Ethics Committee
IRB	Institutional Review Board
ITT	Intent-To-Treat
MedDRA	Medical Dictionary for Regulatory Activities
MMRM	Mixed Model Repeated Measure
PI	Principal Investigator
QoL	Quality of Life
SAE(s)	Serious Adverse Event(s)
SAP	Statistical Analysis Plan
SD	Standard Deviation
SOC	Standard of Care
TEAE	Treatment Emergent Adverse Event
VLU	Venous Leg Ulcer

### 1 Background Information and Scientific Rationale

### 1.1 Chronic Lower Extremity Ulcers

Chronic lower extremity ulcers (CLU) are a common and complicated disease to treat [1], and result in high morbidity [2] and significantly reduced quality of life [3]. Normal wound healing consists of four overlapping phases: hemostasis, inflammation, proliferation, and remodeling [4]. Most ulcers heal when the cause is eliminated, and the ulcer is treated with standard wound care. Some ulcers, however, are for various reasons locked in the inflammatory stage and do not heal [5].

#### 1.2 Rationale

Omeza is a medical technology and consumer healthcare products company specializing in the treatment of chronic hard to heal wounds such as venous leg ulcers, diabetic foot ulcers and pressure ulcers. The Omeza® Products Bundle consists of the Omeza® Lidocaine Lavage, Omeza® Collagen Matrix, Omeza® Skin Protectant. Omeza® oil is the company's platform technology, included in all its products. Omeza oil is unique, because it is anhydrous and contains a proprietary formulation of Omega-3, 6 and 9 oils plus nutrients in a rapidly penetrating delivery system. Omeza is the first value-based wound care company, and the Omeza® bundle of products sets a new standard of care.

The goal of this study is to compare this new line of products, the Omeza® Products Bundle, when used together as directed (see **Appendix 4**) to the standard of care in terms of efficacy and safety for the treatment of chronic venous leg or diabetic foot ulcers.

### 2 Overview of Study Objectives

#### **Primary Objective**

1. To compare the efficacy of Omeza® Products Bundle to standard of care in the treatment of chronic venous leg ulcers and diabetic foot ulcers.

#### Secondary Objective

- 1. To evaluate the safety profile of the Omeza® Products Bundle compared to the standard of care.
- 2. To obtain cost benefit data comparing the Omeza® Products Bundle compared to standard of care in the treatment of chronic venous leg ulcers and diabetic foot ulcers.

#### **Exploratory Objective**

To measure the Quality of Life (QoL) of the subjects with chronic venous leg ulcers and with diabetic foot ulcers.

### 3 Study Design

### 3.1 Description of the Study Design

This is a randomized, multicenter, open-label study comparing the Omeza® Products Bundle versus standard of care treatments for 2 different types of chronic ulcers (venous leg ulcers and diabetic foot ulcers). The treatment period will be 12 weeks, with subjects coming into the study site weekly for evaluations, photography and formal measurements of the target wound, and dressing changes. There will be a total of 13 study site visits. The Screening Visit (Day 0) will occur 1 week prior to randomization and will include routine labs and vascular assessment to determine inclusion/exclusion of the potential subject from the study; followed by weekly treatment visits (Week 1 through Week 11); randomization will occur at Treatment Visit Week 1; the Treatment Visit Week 12/End of Study Visit will include end of study labs. Target wounds will be photographed and measured, and vascular assessment will be done at each of the 13 visits. Standard of care will be billed to subject's insurance for both TEST and SOC.

If the wound closes before Week 12, the subject will continue to come in for all the remaining study visits until study completion. If the wound does not close by Week 12, the subject will be immediately exited from the study and no further follow-up will occur as part of the study.

Table 1: Study Plan

Study Period	Visit	Purpose
Screening	Screening (Day 0)	Determine eligibility, routine labs,
		vascular assessment, photos and
		measures
Baseline /	Treatment Visit Week 1	Review eligibility, randomization,
Randomization		Wound-QoL questionnaire, vascular
		assessment, photos and measures,
		begin study treatments.
Treatment	Treatment Visits Week 2 - Week	Study treatments, vascular assessment,
	11	photos and measures
End of Study Visit	Treatment Visit Week 12	End of Study routine labs, vascular
		assessment, photos and measures,
		Wound-QoL questionnaire

For subject to be eligible they must meet entry criteria. If the subject is not found eligible at Treatment Visit Week 1, the subject may be re-screened once or may be replaced.

### 3.2 Study Endpoints

#### Primary Endpoint:

- 1. Percent Change from Baseline in target wound measure at Week 4, Week 8 and by Week 12.
- 2. Ulcer Size Closure rate at Week 4, Week 8 and by Week 12.
- 3. Time to maximum closure or complete closure.
- 4. Incidence of DFU and VLU healing at Week 12.

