# 10 Statistical Considerations (See Statistical Analysis Plan [SAP])

### 10.1 General Considerations and Populations

The primary endpoint is percent change from baseline in target wound measure by Week 12/End of Study.

All statistical testing will be performed at a two-sided alpha=0.05 level of significance. A detailed Statistical Analysis Plan (SAP) will be finalized prior to database lock.

All subjects who are randomized and receive at least one study treatment will be included in the Safety Population. All summaries of safety data will be based on this population and reported "as treated" – in case there are subjects that were not treated as per the randomization outcome.

All subjects who are randomized, receive at least one study treatment and have at least one post-baseline measure assessment will be included in the Intent-to-Treat Population (ITT). All efficacy summaries will be based on this population and will be reported according to the intent to treat principle (as randomized).

A review of major protocol violations will be performed. Major violations will include, but not be limited to, an assessment of compliance, use of concomitant medications and intercurrent illnesses. Subjects and data points without major protocol violations will be included as part of the Per-Protocol Population. If fewer than 10% of the subjects have major protocol violations, these analyses may not be performed.

All analyses and summaries will be reported overall and for each indication (venous leg ulcers and diabetic foot ulcers).

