## 10.4 Sample Size Rationale

The power of the study is computed for the primary endpoint of "percent change from baseline in target wound measure by Week 12" comparing the two means. The combined sample size of 78 subjects (randomized 2:1) will provide over 80% power to detect a difference of about 14 units (percent change from baseline in wound measure by Week 12), assuming a standard deviation of 20 units, and a 2-sided significance level of 5%.

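### The protocol gives conflicting definitions of the primary endpoint and never says which endpoint, time point and population decides the trial at the 5% level

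*Protocol*

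**What the plan says.** The protocol defines the primary endpoint in three ways.

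- **Four endpoints.** Section 3.2 puts four items under its primary heading: "Percent Change from Baseline in target wound measure at Week 4, Week 8 and by Week 12"; "Ulcer Size Closure rate at Week 4, Week 8 and by Week 12"; "Time to maximum closure or complete closure"; and "Incidence of DFU and VLU healing at Week 12". The synopsis (Statistical Methods) lists the same four as the primary endpoint. The secondary endpoints in 3.2 are only safety and cost benefit, so no efficacy endpoint is labelled secondary there.
- **One endpoint, one time.** Section 10.1: "The primary endpoint is percent change from baseline in target wound measure by Week 12/End of Study". Section 10.4 and the synopsis sample size paragraph use the same endpoint: "The combined sample size of 78 subjects (randomized 2:1) will provide over 80% power to detect a difference of about 14 units", with an assumed SD of 20.
- **One endpoint, three times.** Section 10.2 describes the primary efficacy endpoint as percent change at Week 4, Week 8 and by Week 12, analysed by MMRM.

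On the error level, 10.1 states: "All statistical testing will be performed at a two-sided alpha=0.05 level of significance". On populations, the synopsis states: "Analyses will be performed on each of the two indications (venous leg ulcers and diabetic foot ulcers) and overall". Section 10.1 likewise reports all analyses overall and for each indication.

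**The concern.** The primary objective (section 2) is to compare efficacy in venous leg ulcers and diabetic foot ulcers. On the text as it stands, that objective could be declared met on any of four endpoints, at any of up to three times, in the combined sample or in either indication. A 5% level per test does not give a 5% level for such a claim.

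The sample size supports only the narrowest definition, which 3.2 contradicts. The study is open label, and 10.1 requires the SAP only before database lock, so the protocol is where the decisive result should be fixed. At stake is what counts as a positive trial.

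**Working it through.** **Inputs.** From 10.4: difference 14, SD 20, two-sided 5%, 78 subjects at 2:1, hence 52 TEST and 26 SOC. From the synopsis: 26 TEST and 13 SOC per indication. From 10.1: alpha 0.05 for every test. Correlations between endpoints are not in the protocol and are assumed below.

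**1. The plan's own power figure.** SE = 20 × √(1/26 + 1/52) = 4.80, and 14 / 4.80 = 2.914. Normal power = Φ(2.914 − 1.960) = Φ(0.954) = 83.0%. The noncentral t gives 82.1%. Power above 80% is therefore reproduced for one pooled, unadjusted test.

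**2. Which endpoints have a between-arm analysis.** Section 10.2 names two: the MMRM for percent change, and a comparison of the proportion healed at Week 12. Time to closure gets Kaplan-Meier estimates with median, quartiles and 95% CI. The reduction rate is calculated. The MMRM has treatment and visit but no treatment-by-visit term, so as written it gives one treatment effect, not three.

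**3. Chance of at least one false positive.** With k independent tests it is 1 − 0.95^k: k = 2 gives 9.75%, k = 4 gives 18.5%, k = 8 gives 33.7%. To add the indications, null test statistics were simulated (200,000 runs) with equal correlation between endpoints. The overall statistic was (VLU + DFU)/√2, because the indications are of equal size.

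| Endpoints that may carry the claim | Combined only | Combined + VLU + DFU |
|---|---|---|
| One | 5.0% | 11.5% |
| Two with a named comparison, correlation 0.9 to 0.5 | 7.1% to 9.0% | 15.8% to 20.2% |
| Same two, independent | 9.75% | 21.7% |
| Four in 3.2, correlation 0.9 to 0.5 | 9.4% to 15.6% | 20.4% to 32.7% |
| All 8 endpoint-by-time items, correlation 0.9 to 0.5 | 12.0% to 25.0% | 25.4% to 48.8% |

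The one-endpoint row needs no assumption about correlation between endpoints. The last two rows are upper bounds, because they count items for which step 2 found no test.

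**4. Power if four primaries were kept.** Alpha per test = 0.05 / 4 = 0.0125, critical value 2.498. Normal power = Φ(2.914 − 2.498) = Φ(0.416) = 66%; the noncentral t gives 63.9%. Restoring 80% would need about 105 subjects rather than 78.

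**The case against.** The strongest defence is that 10.1, 10.4 and the synopsis sample size paragraph agree on percent change by Week 12, and the last two size it on the combined sample. If that comparison governs, its 5% level is correct and its power reproduces. The heading of 10.2 refers to both primary and secondary analyses, which suggests that some items were meant as secondary. The protocol states 0.05 as a level for tests and never claims family-wise control. Ordering rules and alpha allocation are commonly left to the SAP.

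Most of this stands, and a missing multiplicity procedure is not the point here. It does not remove the contradiction: 3.2 and the synopsis label all four endpoints primary, and 3.2 leaves no efficacy endpoint as secondary. A reader cannot tell from the protocol which definition prevails.

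A reader might also infer more than the text supports:

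- **That 8 items are each tested in three populations, 24 tests in all.** Section 10.2 names no between-arm test for closure rate or time to closure, and its MMRM yields one treatment effect. The synopsis efficacy criteria do present all four endpoints as comparing the arms, so the larger counts serve as upper bounds and no more.
- **That low power within an indication is an error.** At 26/13, power for 14 units is 51.9% (noncentral t), but 10.4 says openly that the sample is combined, so no stated figure is contradicted. Nor does any rule require a win in both indications.

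**Conclusion.** The point holds as an internal contradiction with consequences for the error rate. Section 3.2 and the synopsis give four primaries, 10.2 gives one at three times, and 10.1 with 10.4 gives one by Week 12. No statement says which endpoint, time point and population is decisive.

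The excess over 5% is conditional: it arises if any of the candidate results may carry the claim. It is then about 11.5% on the mildest reading with more than one population (one endpoint, three populations), and about 16% to 22% for the two endpoints actually compared. The second range rests on assumed equal correlations from 0.9 to 0. It cannot be said that the 5% level fails outright, because the single pooled test in 10.1 and 10.4 is valid at 5% with about 82% power. This should be corrected before the trial is analysed, because it determines what a positive result means.

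**What to change.** Align 3.2, the synopsis and 10.2 with 10.1 and 10.4:

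- Name one primary endpoint: percent change from baseline in target wound measure at Week 12, in the combined population. Writing at instead of by Week 12 in every place ties it to one visit, and 10.2 should identify the Week 12 treatment contrast as the primary comparison.
- Move closure rate, time to closure and proportion healed to secondary endpoints.
- Make Weeks 4 and 8 supportive.
- Report VLU and DFU results as estimates with 95% CIs, not as separate primary claims.

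The cost is a protocol wording amendment and fewer stand-alone claims. No subjects are added and the stated power is kept. The order of the secondaries, adjustment for indication and a statement of per-indication power are optional and not part of this error.

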#### Secondary Endpoint:

- Safety and tolerability will be evaluated by assessing Treatment Emergent Adverse Events, Treatment Compliance, Concomitant Medications, Clinical Laboratory Findings, Vital Signs and Physical Examinations.
- 2. To obtain cost benefit data comparing the Omeza Product Bundle and Standard of Care in treatment of the ulcers.

#### **Exploratory Endpoint:**

A questionnaire called "Wound-QoL" will be used to measure the quality of life.

### 4 Study Population

#### 4.1 Recruitment Plan

The subjects will be enrolled at up to 3 study sites from the patient population of board certified actively licensed physicians, who have demonstrated clinical research experience and/or possess an NIH or CITI training certificate and who have been qualified as Principal Investigators (PI) by the Contract Research Organization (CRO).

### 4.2 Subject Entry Criteria

Population: Male and Female subjects suffering from chronic venous leg ulcers or Diabetic foot ulcers

\_\_\_\_\_

### Eligibility Criteria Venous Leg Ulcer (VLU):

#### **Inclusion Criteria:**

- 1. Male or female 21-80 years of age
- Participated in the informed consent process and signed study specific informed consent document
- 3. Willing and able to comply with study procedures, including study visits and study dressing regimens
- 4. Confirmation of venous disease by non-invasive venous studies with either Doppler-confirmed venous reflux or having ≥ 2 clinical characteristics of venous insufficiency (varicose veins, lipodermatosclersosis, venous dermatitis, atrophie blanche, edema). Biopsy done to exclude other skin conditions e.g. cancer on ulcers ≥ 6 months
- 5. HbA1c of ≤ 10%
- 6. Have a venous ulcer between the knee and ankle, at or above the malleolus
- 7. Target wound size ≥4 cm² to ≤ 150 cm² in area without exposed tendon, muscle or bone
- 8. Target wound duration of at least 3 months and less than or equal to 12 months as of the date the subject signs consent for study
- 9. VLU may have characteristics that include yellow/white slough with or without fibrous/scar tissue and/or non-viable tissue, but not mandatory
- 10. Be willing and able (or have family member/friend willing and able) to apply required dressing changes as well as the ability of the subject to tolerate limb compression bandage

